### 3. STUDY DESIGN

#### 3.1 Study Overview

This is a single institution, open label, single-arm phase 2 trial. We plan to accrue up to 50 subjects in order to meet our goal of 29 evaluable subjects. Each subject will be administered Tazemetostat orally twice daily for subjects with recurrent and/or metastatic MPNST. Subjects will be dosed in continuous 28 day cycles, and as follows:

- Pediatric (12y- <18y): 520 mg/m^2/dose orally BID, not to exceed 800 mg orally twice daily
- Adult: ( $\geq 18$ y): 800 mg orally BID (flat dose for adults)

Surveillance imaging of primary and metastatic sites will be performed every 2 cycles, +/- 7 days after Cycle 1 Day 1, until disease progression or death. ctDNA testing results will be collected whenever performed per standard of care.

Response to treatment will be evaluated via RECIST 1.1. Treatment with Tazemetostat will continue until disease progression, unacceptable toxicity or withdrawal of consent or termination of study. Screening data will be reviewed to determine subject eligibility. Subjects who meet all inclusion criteria and none of the exclusion criteria will be entered into the study.

Total duration of subject participation will be 24 months. Total duration of the study is expected to be 36 months.

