## 6.1 Schedule of Events

Procedure:	Visit:	SCREENING (Windows outlined in Section 6.2)	CYCLE 1	CYCLES 2 AND BEYOND (WITHIN 72 HRS PRIOR)	END OF TREATMENT (WITHIN 14 DAYS OF LAST STUDY DRUG ADMINISTRATION)	FOLLOW UP (28 +/- 7 DAYS AFTER LAST DOSE OF TREATMENT)	SURVIVAL FOLLOW UP EVERY 90 +/- 14 DAYS AFTER LAST DOSE
Informed Consent		X					
Medical History, Demographic Information		X					
Clinical Exam		X	X	X	X		
Performance status (PS) 		X	X	X	X		
Vital Signs (VS) including height  , weight, and BSA 		X	X	X	X		
Numbered Pain Rating Scale 			X	X	X		
Labs (CBC diff, CMP) 		X	WEEKLY 	X			X 
Pregnancy Test (Urine or Serum) 		X	X	X			
INR		X					
Tibial x-ray 		X		X 			
Provide Study Drug for home administration			X	X			
Tumor disease evaluation 		X		EVERY 2 CYCLES 	X		
Tumor NGS 		X					
Circulating tumor DNA (ctDNA) 				X	X		
Provide and/or Review Subject Diary			X	X	X		
Concomitant Medication Review 		X	X	X	X		
Adverse Event Review 			X	X	X	X	
Survival Assessment							X

Abbreviations: VS=vital signs (blood pressure, temperature, pulse and respiratory rates, weight and height); CBC/diff=complete blood count and white blood cell differential; CMP = complete metabolic profile (sodium, potassium, chloride, bicarbonate, blood urea nitrogen, creatinine, glucose, alkaline phosphatase, AST, ALT, total bilirubin, protein), NGS Next Generation Sequencing

1 Performance status: Pediatric Karnofsky for subjects  $\geq$  16 years of age and Lansky for subjects 12-15 years of age; Adult ECOG score (18+)

UF-SC-001

2024-Aug-12

- 2 Numbered Pain Rating Scale , refer to Appendix G.
- 3 Laboratory tests at baseline need not be repeated if therapy starts within 72 hours of obtaining labs to assess eligibility. Labs are to be collected weekly for Cycle 1 (Days 1, 8, 15, and 22) +/- 72 hours. If patients have Grade 4 neutropenia then CBCs should be checked at least every other day until recovery to Grade 3 or until meeting the criteria for dose limiting toxicity. Automated differentials acceptable unless concern for blasts; then please obtain manual differential.
- 4 Female subjects of childbearing potential only.

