- 5 Patients must have either CT or MRI of primary and metastatic tumors, as well as whole body 18F-FDG PET/CT. Radiographic Tumor Assessment using RECIST 1.1 criteria. Imaging to be obtained every 2 cycles +/- 7 days from Cycle 1 Day 1 until disease progression or death. Screening imaging studies must be obtained within 30 days prior to start of protocol therapy.
- 6 Tumor NGS will be sent as part of standard of care, if not already done. If already done, results will be recorded as part of medical history review.
- 7 Circulating tumor DNA (ctDNA) results will be collected whenever obtained per standard of care.
- 8 Height and BSA only collected for pediatric subjects.
- 9 Adverse events, comed collection, and all sample collections, should be performed pre-dose at every cycle. The study drug will be provided at study visits, but self-administered at home throughout the trial. Cycles may be repeated for up to a total duration of therapy of 2 years (maximum 26 cycles), provided the patient meets the criteria for starting subsequent cycles and does not meet any of the criteria for removal from protocol therapy criteria.
- 10 Only to be completed for subjects <18 years of age. Screening tibial x-ray may have been performed within the past 6 months (180 days) before treatment (C1D1).
- 11 Tibial x-rays to be completed every 180 +/- 30 days only for those with open growth plates at screening.
- 12 CBC only – at each survival follow-up visit for five years, then yearly (at least once per calendar year) up to 10 years. Once a subject begins new anti-cancer therapy, they will be followed for survival only.

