## 6.2 Allowable Visit Windows

Visit Name	Window
Screening	
Informed Consent	≤ 28 days prior to Cycle1 Day 1 (C1D1)
Medical History, Physical examination, Performance Status, Concomitant Medications, and Labs (CBC Diff, CMP, INR, pregnancy test)	≤ 28 days prior to Cycle1 Day 1 (C1D1)
Tibial X-Ray	≤ 180 days prior to Cycle1 Day 1 (C1D1)
Imaging (CT and PET)	≤ 30 days prior to Cycle1 Day 1 (C1D1)
All other screening procedures	≤ 7 days prior to C1D1
Cycle 1 Day 1	
Labs	Laboratory tests at screening need not be repeated if therapy starts within 72 hours of obtaining labs to assess eligibility. All others to be done ≤ 72 hours of C1D1 dosing. Labs are to be collected weekly for Cycle 1 (Days 1, 8, 15, and 22) +/- 72 hours
All other baseline procedures (which include complete physical exam, performance status, vital signs, and concomitant medication review)	Baseline procedures completed at screening need not be repeated if therapy starts within 72 hours of performing procedures to assess eligibility. All others to be done ≤ 72 hours of C1D1 dosing.
Day 1 of subsequent cycles (after Cycle 1)	
Assessments	Within 72 hours prior to dosing
Study treatment administration (dosing)	Every 28 days
Tibial X-Ray	Every 180 +/- 30 days
Tumor Assessments	Imaging every 2 cycles +/- 7 days from Cycle 1 Day 1 until disease progression or death.
End of Treatment (EOT) Procedures	Within 14 days of last dose of therapy
28-Day Safety Follow-up	28 +/- 7 days after last dose of treatment

Survival Follow-Up	Every 90 +/- 14 days
--------------------	----------------------

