#### 6.3 End of Treatment Evaluations

The end of treatment visit as well as evaluations will occur within 14 days following the last dose of therapy. End of treatment evaluations will also be performed within 14 days if the subject is discontinued as per section 8.2.

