#### 6.4 Follow up/ Evaluations

Subjects will have a follow-up visit for the evaluation of adverse events 28 days ( $\pm$  7 days) after the last dose of study medication. Any adverse events ongoing at the follow up visit will be followed until resolution or start of a new therapy. If the subject is unavailable to travel to the institution, the visit may be made via telephone interview to review for adverse event resolution or the occurrence of any new adverse events. Additionally, external or internal medical records may be consulted with permission of the subject to complete remote visit reporting.

Subjects will continue to be contacted via telephone for survival approximately every 90 +/- 14 days until death. Safety labs (CBC) will be performed as part of these visits for 5 years, then annually until 10 years (at least once per calendar year) after last dose of therapy. Labs may be collected at an outside laboratory as standard of care. If study therapy is discontinued for reasons other than progression, continue imaging/disease assessments per standard of care until progression or until start of another therapy or death. Following discontinuation of study therapy for any reason, report the date the first non-protocol anti-cancer therapy is administered. Once a subject begins new anti-cancer therapy, the subject will be followed for survival only.

If a subject becomes unreachable during the course of the study, the investigator or study team will make a reasonable effort to contact the subject and document each attempt (in accordance with Section 4.3.4 of the ICH E-6 GCP). If these attempts are not successful, the subject may be declared "lost to follow up." For subjects lost to follow-up, the termination date will be the date of last contact with the subject.

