### 7.2 Overview of treatment plan

Tazemetostat will be administered at a dose of 520 mg/m^2/dose for pediatric patients 12- < 18 years of age (rounding up if between doses), and for adults  $\geq$  18 years of age, 800 mg, orally twice daily. The powder for suspension must be reconstituted prior to administration. Patients can take Tazemetostat without regard to meals, with no less than 8 hours between each dose. The oral suspension should be given by mouth immediately after the dose is prepared in the oral syringe. Patients should drink additional water after administration (about 4 ounces). For feeding tube dosing, administer directly into the feeding tube with the syringe. Rinsing with 10 mL of water for NG tubes and 40 mL of water for G-tubes is recommended. If vomiting occurs after taking oral suspension formulation, the dose should NOT be repeated and the next dose should be administered at the regularly scheduled time.

Therapy will be discontinued if there is evidence of progressive disease or drug related dose-limiting toxicity that requires removal from therapy (Section 7.6). A cycle of therapy is considered to be 28 days. Cycles may be repeated for up to a total duration of therapy of 2 years (maximum 26 cycles), provided the patient meets the criteria for starting subsequent cycles and does not meet any of the criteria for removal from protocol therapy criteria.

Pediatric drug dosages should be adjusted based on the BSA calculated from height and weight, measured within 7 days prior to the beginning of each cycle. Patients who experience dose-limiting toxicity should have their dose reduced by 25% so that patients receive 75% of the original administered dose.

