### **Evaluation of Best Overall Response**

The best overall response is the best response recorded from the start of the study treatment until the earliest of objective progression or start of new anticancer therapy, taking into account any requirement for confirmation. The subject's best overall response assignment will depend on the findings of both target and non-target disease and will also take into consideration the appearance of new lesions. The best overall response will

be calculated via an algorithm using the assessment responses provided by the investigator over the course of the trial.

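### For subjects who stop drug without progression the protocol gives two imaging rules, so PFS, TTP and the stable-disease part of CBR can be ascertained at uneven intervals

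*Combined protocol and SAP*

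**What the plan says.** Protocol section 3.1 schedules surveillance imaging "every 2 cycles, +/- 7 days after Cycle 1 Day 1, until disease progression or death". Section 6.1, footnote 5, repeats it: "Imaging to be obtained every 2 cycles +/- 7 days from Cycle 1 Day 1 until disease progression or death". Section 6.2 has the same rule, "Imaging every 2 cycles +/- 7 days from Cycle 1 Day 1 until disease progression or death", in the block for Day 1 of cycles after the first. Section 7.2 fixes the unit: "A cycle of therapy is considered to be 28 days".

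Section 6.4 covers subjects whose therapy ends for reasons other than progression. The site is to "continue imaging/disease assessments per standard of care until progression or until start of another therapy or death". No interval is given, and the start of another therapy is added as an end point. After new therapy, follow-up is for survival only.

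In the section 6.1 grid, the row "Tumor disease evaluation" is marked at screening, every 2 cycles and End of Treatment. Both follow-up columns are blank. Section 6.3 secures the last of these scans for early stoppers: "End of treatment evaluations will also be performed within 14 days if the subject is discontinued as per section 8.2".

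Section 2.2.2 runs PFS and TTP from start of treatment to RECIST progression (PFS also to death) and counts stable disease toward CBR if it lasts at least 4 months. On response, Appendix C says "The best overall response is the best response recorded from the start of the study treatment until the earliest of objective progression" or the start of new anticancer therapy. Section 12.4 censors event-free survivors at the last follow-up date.

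**The concern.** The protocol itself creates a group that is off drug and progression-free: subjects removed for unresolved or recurrent dose-limiting toxicity (7.6.2, 7.6.4), subjects who reach the 26-cycle cap (7.2), and those who stop for the other reasons in 8.2. For them PFS, TTP, CBR and best overall response all remain open after the last dose, but the protocol does not settle when they are scanned. Counting in cycles also gives no clear date once cycles have ended.

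If standard-of-care scans are sparser than 8-weekly, progression is recorded later in these subjects than in those still on treatment, for a reason unrelated to their disease. Stable disease at 4 months may be left unverified. Scans not taken at the time cannot be recovered at analysis.

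**Working it through.** **1. The design figures.** Inputs from section 12.2: 9 subjects in stage 1, stop at 2 or fewer responses; 29 in total, reject at 10 or more; ORR 21% under the null, 45% under the alternative. The probability of rejection is the sum over x = 3 to 9 of Bin(9, x; p) × P[Bin(20, p) ≥ 10 − x].
- p = 0.21: 0.0485 (stated 5%).
- p = 0.45: 0.804 (stated 80%).

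The plan's figures reproduce. The imaging rules do not enter them.

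**2. The rules side by side, off drug without progression.**

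| Place | Interval | Ends at |
|---|---|---|
| 3.1 | 2 cycles = 2 × 28 days = 8 weeks | progression or death |
| 6.1, footnote 5 | 8 weeks | progression or death |
| 6.2 (under an on-treatment heading) | 8 weeks | progression or death |
| 6.4 | none given | progression, other therapy or death |
| 6.1 grid | no scan after End of Treatment | – |

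Footnote 5 belongs to the grid row whose follow-up columns are blank, so section 6.1 is also at odds with itself.

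**3. Effect by endpoint.**
- *ORR:* a response present when drug stops is captured by the End of Treatment scan. Only a first response that appears later, before new therapy, depends on off-drug imaging.
- *CBR:* take a subject removed at week 10. The End of Treatment scan falls by week 10 + 2 = 12. Four months is about 4 × 365.25/12/7 = 17.4 weeks. An 8-weekly grid has scans due at weeks 16 and 24; section 6.4 names no date.
- *PFS and TTP:* progression is dated at the scan that shows it, so the interval matters directly.

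**4. Size of the delay (illustration only).** Assumptions: exponential time to progression with a median of 17 weeks (the median PFS of the adult series cited in section 1.2); regular scans; no deaths or symptom-prompted scans. The documents give no standard-of-care interval, so d is varied. With λ = ln 2/17 = 0.0408 per week, 1/λ = 24.53 weeks and

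mean delay = d/(1 − exp(−λd)) − 1/λ.

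| d (weeks) | d/(1 − exp(−λd)) | Mean delay | Added to 8-weekly |
|---|---|---|---|
| 8 | 28.74 | 4.2 | 0 |
| 12 | 31.01 | 6.5 | 2.3 |
| 16 | 33.39 | 8.9 | 4.6 |

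**5. Censoring.** After treatment, subjects are contacted by telephone about every 90 days (6.4). A subject with no scan since End of Treatment who is reached twice has a last follow-up date about 2 × 90 = 180 days (26 weeks) after the last dose, yet the disease was last assessed within 14 days of that dose. Under section 12.4 the whole interval counts as progression-free.

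**The case against.** The best defence is that section 6.4 is the specific rule for subjects off drug and the rest describe treatment. The placement of the line in 6.2 supports this. Section 3.1 and footnote 5 carry no such limit, however, and even on this reading the off-drug interval is undefined.

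The affected group may be small. Section 1.4.1 reports 5% stopping for treatment-related adverse events in a follicular lymphoma study, which would be 0.05 × 29 = 1.5 subjects; section 1.4.2 reports none stopping for treatment-emergent events in mesothelioma. Under the step 4 assumption, the share progression-free at 26 cycles (104 weeks) is 0.5^(104/17) = 1.4%, or 0.4 of 29. PFS and TTP are secondary and descriptive, with no comparator arm. All this stands and limits the weight of the point.

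A reader might infer more than the documents support:
- *That these subjects have no scan in the schedule once drug stops.* The End of Treatment scan is marked, and section 6.3 extends it to early stoppers.
- *That a site cannot satisfy both rules.* Standard of care has no stated interval; a site scanning 8-weekly would meet both until new therapy starts.
- *That on-treatment scans drift when cycles are delayed.* Imaging is anchored to Cycle 1 Day 1 with a 7-day window, and toxicity unresolved at 14 days means removal.
- *That the primary endpoint is materially biased.* The documents give no frequency for first responses arising after drug stops.

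**Conclusion.** The conflict is real and should be resolved. It bears on PFS, TTP and the stable-disease part of CBR. The effect on ORR is small, and the Simon design is untouched.

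The size is conditional. Added mean delay is zero if standard of care is 8-weekly, and about 2 to 5 weeks per affected subject at assumed intervals of 12 to 16 weeks, set against a 17-week median. Deaths and symptom-prompted scans would shorten it. The documents state neither the interval nor the number affected, so no figure for the bias in the trial's PFS estimate can be given. Censoring at last follow-up aggravates the problem, because telephone contact without imaging adds progression-free time.

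**What to change.** Adopt one calendar-based rule throughout: tumor assessment every 8 weeks +/- 7 days from Cycle 1 Day 1, regardless of dosing status, until progression, new anti-cancer therapy or death. The interval is the protocol's own 2 cycles of 28 days.
- State it in 3.1, footnote 5 and 6.2, and use it in 6.4 in place of the standard-of-care wording.
- Extend the tumor-evaluation row of the 6.1 grid into follow-up for subjects without progression.
- In 12.4, censor PFS and TTP at the last adequate tumor assessment rather than the last follow-up date.

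The cost is a wording amendment, a table entry and some follow-up scans in the few subjects who stop without progression, including whole-body PET/CT if footnote 5 is applied in full. Sections 3.1 and 6.1 already require these scans as written.

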### 7. STUDY TREATMENT

#### 7.1 Treatment Schedule/Administration

Tazemetostat will be administered orally twice daily with the dose beginning at the baseline visit (Cycle 1/Day 1) according to the Table 2 below.

Table 2: Tazemetostat Dosing

Baseline Criteria (age at enrollment)	Dose (continuous 28-day cycles)
Pediatric (12y - < 18y)	520 mg/m  /dose orally twice daily, not to exceed 800 mg orally twice daily, rounded up if between doses
Adult ( $\geq$ 18y)	800 mg orally twice daily (flat dose for adults)

### 7.2 Overview of treatment plan

Tazemetostat will be administered at a dose of 520 mg/m^2/dose for pediatric patients 12- < 18 years of age (rounding up if between doses), and for adults  $\geq$  18 years of age, 800 mg, orally twice daily. The powder for suspension must be reconstituted prior to administration. Patients can take Tazemetostat without regard to meals, with no less than 8 hours between each dose. The oral suspension should be given by mouth immediately after the dose is prepared in the oral syringe. Patients should drink additional water after administration (about 4 ounces). For feeding tube dosing, administer directly into the feeding tube with the syringe. Rinsing with 10 mL of water for NG tubes and 40 mL of water for G-tubes is recommended. If vomiting occurs after taking oral suspension formulation, the dose should NOT be repeated and the next dose should be administered at the regularly scheduled time.

Therapy will be discontinued if there is evidence of progressive disease or drug related dose-limiting toxicity that requires removal from therapy (Section 7.6). A cycle of therapy is considered to be 28 days. Cycles may be repeated for up to a total duration of therapy of 2 years (maximum 26 cycles), provided the patient meets the criteria for starting subsequent cycles and does not meet any of the criteria for removal from protocol therapy criteria.

Pediatric drug dosages should be adjusted based on the BSA calculated from height and weight, measured within 7 days prior to the beginning of each cycle. Patients who experience dose-limiting toxicity should have their dose reduced by 25% so that patients receive 75% of the original administered dose.

### 7.3 Criteria for Starting Subsequent Cycles

A cycle may be repeated every 28 days if the patient has at least stable disease and has again met laboratory parameters as defined in the eligibility section (Section 4) and remains eligible to continue agent administration per the

requirements in the Investigator Brochure, package insert, and Sections 4 and 7 of this document.

#### 7.4 Grading of Adverse Events

Adverse events (toxicities) will be graded according to version 5.0 of the NCI Common Terminology Criteria for Adverse Events (CTCAE). All appropriate treatment areas should have access to a copy of version 5.0 of the CTCAE. A copy of the CTCAE v5 can be downloaded from the CTEP website (<http://ctep.cancer.gov>). Any suspected or confirmed dose-limiting toxicity should be reported immediately (within 24 hours) to the Project Management Office ([[contact]](mailto:[contact])) and the PI.

#### 7.5 Supportive Care and other concomitant therapy

##### 7.5.1 Supportive Care Guidelines

Subjects should receive full supportive care, including transfusions of blood and blood products, antibiotics, antiemetics, antidiarrheals, analgesics, etc., when appropriate. Bisphosphonates or denosumab are allowed for subjects with bone metastases.

Growth factors that support platelet or white cell number or function can only be administered for culture proven bacteremia or invasive fungal infection when approved by the Principal Investigator.

##### 7.5.2 Concomitant Therapy

Relevant medical history should be obtained at screening and include prior medications and treatment history. All medications taken within 4 weeks prior to screening, regardless of indication, should be recorded.

Any therapy or medication (except study drugs), administered from screening until thirty days after the last dose of either study drug, is considered a concomitant therapy or medication. However, if another course of anti-cancer therapy is initiated prior to the thirty-day follow-up period visit, a record of concomitant medications will no longer be performed. If the use of any concomitant treatments (medications or procedures) becomes necessary, the treatment must be recorded, including the name of the drug or treatment, dose, route, date, indication for use, expected duration, and frequency of treatment.

Assessment and documentation of concomitant medications will be done at each visit.

